Pulpotomy is considered the gold standard procedure for treating cariously exposed pulps in asymptomatic primary teeth. Which is based on the healing ability of the radicular pulp tissue following amputation of the infected coronal pulp. (5)

Mineral trioxide aggregate (MTA) has been recommended as the gold standard for vital pulp therapy; however, it has some disadvantages, such as long setting time, poor handling properties, high cost, and the potential for tooth discoloration. Biodentine (Septodont, Saint-Maur-des-Fossés, France), one of the new-generation, bioactive endodontic cements, has been claimed to have improved properties over MTA.

Biodentine presents high biocompatibility with the dental pulp, it has high antibacterial effects and antifungal activity, has a shorter setting time than MTA as a result of the calcium chloride in the liquid component of Biodentine. It also has higher flexural strength, compressive strength and modulus of elasticity than MTA. Consequently, Biodentine can be used as a pulp dressing as well as a base material. (6)

Quest is on for newer pulpal medicaments that are biocompatible and capable of healing the dental pulp by producing reparative dentin and/or dentinal bridge in response to various stimuli and surgical exposure.

Collagen has a proven rate of success in the field of dentistry as guided tissue regeneration, root conditioning, hemostatic, and wound dressing agent. It has inherent properties like low immune response and toxicity, ability to promote cellular growth and attachment, homeostasis, and added advantage of antibiotic incorporation. (7)

7. Objectives:

Aim of the study

To assess clinical and radiographic success after collagen based pulpotomy versus Biodentine pulpotomy in children with cariously exposed vital primary molars.

Hypothesis:

Null hypothesis: No added benefits will be gained from the collagen based pulpotomy clinically and radiographically.

PICO approach:

P: Population: Children 4-7 years with carious vital primary molars.

I: Intervention: Sterile medicated Collagen particles.

C: Control: Biodentine.

O: Outcome:

Outcome		Method of measurement	Unit
1ry outcome: Clinical success	1- Absence of internal root resorption	Periapical X-ray (parallel technique)	Binary
2ry outcome:	1- Absence of pain	Questioning the patient	Binary
	2- Absence of swelling	Visually by intraoral and extraoral examination	Binary

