	3- Time elapsed till final restoration performed	Stopwatch	Continuous outcome measured in minutes

(S) Study design: Randomized controlled.

(T) Time of follow up:6 months.

8. Trial design:

Randomized controlled trial (R.C.T).

III. Methods

A) Participants, interventions & outcomes:

9. Study settings:

This study will be carried out on patients attending the out-patient clinic in Pediatric Dentistry and Dental Public Health Department-faculty of Dentistry, Cairo University, Egypt.

The procedure will be carried out by postgraduate student [name], B.D.S(2014)-Pharos University in Alexandria (PUA) and without an assistant.

10. Eligibility criteria:

Inclusion criteria:

- Children:

- 1- Aged 4 to 7, in good general health and medically free.
- 2- Cooperative patients who will comply to follow ups.
- 3- Parents provided with written informed consent.

- Teeth:

- 1- Bilaterally Carious vital primary molars with reversible pulpitis.
- 2- Restorable teeth with no more than 1/3 of root resorption.

Exclusion criteria:

- Children:

- 1- Children with medical, physical, or mental conditions.
- 2- Unable to attend follow up visits.

- Teeth:

- 1- Primary molars with any congenital anomalies.
- 2- Previously accessed teeth.
- 3- At operative procedure, haemorrhage control is unachievable after pulpotomy.

11. Interventions

The principal investigator will carry out all treatment procedures, using the split mouth technique, meaning that both groups (I & II) will be in the same patient.

For both interventions:

1. Informed consent from participating parents.
2. Baseline records photographs, percussion test, periapical radiograph, and personal data collection (Appendix 1: Diagnostic chart).
3. Allocation (concealed by withdrawing a sealed opaque envelope containing eight times folded paper containing the type of dressing material that will be used then writing patient name and ID on it and will be opened after performing the access cavity).
4. Diagnostic chart with personal, medical, and dental history will be filled (Appendix 1: Diagnostic chart).
5. Clinical examination will be performed to assess the clinical inclusion criteria. (Pulpal and periapical diagnosis is established after clinical examination).
6. Preoperative and Postoperative photographs will be taken.

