7. The radiographic examination will be performed by taking periapical x-ray using (parallel technique) through machine to assess the inclusion criteria. The preoperative radiograph will serve as a reference for the follow-up radiographs. Standardization of the technique to avoid any distortion in the vertical dimension and to provide reproducible images using x-ray holding device.
8. Preoperative and postoperative radiograph will be taken by parallel technique using XCP film holder (Super Bite, Hawe Neos Dental SA, Switzerland).
9. Administration of inferior alveolar nerve block (Septodont, Scandonest® 2% L Mepivacaine HCl. 2% and Levonordefrin 1:20,000 Injection, U.S.P.) at the side of the affected tooth.
10. Application of rubber dam for isolation, then a standardized pulpotomy procedure will be performed using a large sterile round end bur in a high-speed handpiece with copious irrigation, a sharp spoon excavator will remove pulpal tissues to the orifice level. Hemostasis will be achieved by the application of a wet cotton pellet to achieve complete hemostasis.
11. Children will then be allocated into either one of the groups alternatively depending on the pulpotomy medicament used as follows:
Group I (Experimental group) collagen based pulpotomy.
Group II (Control group) Biodentine pulpotomy.

Group I (Experimental group) collagen based Pulpotomy:

1. Collagen based pulpotomy will be applied (sterile medicated collagen particles, Biofil-AB, Eucare Pharmaceuticals Pvt. Ltd, Chennai, India) according to the manufacturer's instructions and gently placed over the pulp stumps to a thickness of 2 mm.

Group II (Control group) Biodentine pulpotomy:

1. Biodentine (Septodont, Saint-Maur-des-Fossés, France) will be applied according to the manufacturer's instructions and placed over the radicular pulp with the help of a suitable sterile amalgam carrier. Gentle condensation of the mix will be done in the pulp chamber with a moistened cotton pellet.

12. For both groups;

The rest of the pulp chamber will be filled with glass ionomer cement.

Tooth will then be restored with stainless steel crown (3M ESPE, St Paul, MN, U.S.A.).

12. Outcomes:

Primary outcome:

Absence of periapical radiolucency and internal/ external root resorption (Binary outcome detected with periapical x-ray by Parallel technique using XCP film holder (Super Bite, Hawe Neos DentalSA, Switzerland).

Secondary outcome:

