1- Survival rate (absence of any complication or complementary treatment) in terms of:

1-Absence of spontaneous pain. (Binary outcome measured with direct questioning to the patient).

2-Absence of swelling. (Binary outcome measured visually by intraoral/extraoral examination).

2- Time elapsed till final restoration performed.

13. Participant timeline:

Patients will be diagnosed to determine whether they are eligible for the inclusion criteria of this study or not.

Eligible patients will then start their treatment on the same visit.

	STUDY PERIOD					
	Enrolment	Allocation	Treatment visit	Post-treatment	Close-out	
TIMEPOINT	-t1	0	0	T1 (3m)	T2 (6m)	
ENROLMENT:						
Eligibility screen and patient selection	X					
Informed consent from participating pts	X					
Allocation (concealed in closed white envelop)	X					
INTERVENTIONS:						
The pulpotomy procedure (gaining access to the pulp)		X				
Allocation of the patient to one of the treatments groups (open the closed white envelope)		X				
Application of pulp dressing material (collagen and Biodentine)			X			
Final restoration			X			
ASSESSMENTS:						
baseline variables	1- photographs	X		X	X	X
	2- percussion test	X		X	X	X

	3- preoperative periapical radiograph	X				
	4- personal data	X				
outcome variables	Calculation of time-elapsed till final restoration			X		
	Questioning the patient about the absence of spontaneous pain	X			X	X
	Visual examination of patient to check the absence of sinus or Swelling	X			X	X
	Periapical radiograph to check the absence of periapical radiolucency, internal/ external root resorption	X		X	X	X

14. Sample size:

Sample size will be calculated.

15. Recruitment:

Patients attending the out-patient clinic in the pediatric dentistry department- Cairo University, having bilateral carious lower molars will be carefully assessed for eligibility to participate in our study by one of the main investigators [name], then a full explanation of the nature of our experiment and the importance of maintaining this primary tooth and restoring it for proper functions and the drawbacks of extracting it. Full mouth treatment will be offered for them.

B) Assignment of interventions:

16. Allocation:

16a. Random sequence generation (Randomization):

Teeth that will be included in the current trial will be randomly assigned one of the experimental groups using closed white envelopes (simple randomization 1:1 ratio).

a) Sequence generation:

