By shuffling the envelopes then selecting envelop for each patient upon their enrolment.

b) Allocation Concealment:

Using 8-time folded paper on which dressing material was written contained in the closed white envelope.

c) Implementation:

When a patient agrees to participate in the trial, an envelope will be drawn by one of the residents present at the clinic and name, telephone number and patient's ID will be written on it. Those selected envelopes will be opened at treatment visit after performing pulpotomy to choose which material should be used.

Randomization and allocation concealment will be performed by the co-supervisor to avoid selection bias.

17. Blinding:

The blinding is not possible (unfortunately) due to the nature of the trial.

Trial participants, outcome assessors and statistician will be blinded.

C)Data collection, management, and analysis:

18. Data collection methods

Baseline data collection

Plans for assessment and collection of outcomes will be at 3 and 6 months clinically (using visual examination, palpation, and percussion test with back of the mirror) and 0 and 6 months radiographically (using periapical radiograph) and will be done by two blinded assessors independently, and differences will be solved by consensus. To promote data quality, duplicate measurements by the same examiner (intra-examiner agreement) and training of assessors (inter-examiner agreement) will be done.

19. Data management:

Data will be recorded on a diagnostic chart for each patient separately and will be stored with follow up periapical radiographs.

20. Statistical methods:

Clinical and radiographic outcomes will be submitted for statistical analysis by the Statistical Package for Social Science (SPSS) program windows version 13. Results will be calculated using risk reduction (R.R.).

D) Data monitoring:

21. Monitoring

The study work results will be monitored regularly by the supervisors who will have full access to these interim results make the final decision to terminate the trial.

22. Harms

- **Bur breakage:** the bur will be replaced by a new one and treatment will be proceeded.
- **Perforation of pulpal wall or floor:** The tooth condition and size of perforation will be assessed whether the treatment will be to repair the perforation and treatment will be proceeded (the tooth will be removed from the trial) or the tooth will be extracted, and space maintainer will be performed

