- **No reported hypersensitivity from both tested materials.**
- **Failure of pulpotomy procedure:** retreatment of the tooth through partial pulpectomy and tooth will be removed from the trial.

23. Auditing

The study supervisors will regularly assess the trial process and documents. They will be involved in participant enrolment, consent, eligibility and allocation to study groups, adherence to trial interventions and policies to protect participants, including reporting of complications and their treatments. Clinical procedures will be performed under their supervision.

IV. Ethics and dissemination

24. Research ethics approval:

This protocol, the template and specific informed consent forms (local language and English versions) will be reviewed, approved, and agreed upon by the (Research Ethics Committee) will review all the nature of interventions and will have the right to modify the study methods.

25. Protocol amendments:

The Ethics Committee will be notified of any administrative changes or modifications of the protocol. Any required changes during the trial period for the patient's own interest that might affect the conduct of the study, including changes of the study objectives, study design, patient population, sample sizes, intervention procedures will require a formal amendment to the protocol. Such amendment will be agreed upon by the Council of the Department of Pediatric Dentistry, Faculty of Dentistry, Cairo University.

26. Informed consent:

The investigator will discuss the trial with the legal guardian of each participating child:

- Verbal permission will be taken orally from participating child.
- Written informed consent will be taken from the legal guardian of each participating child willing to participate in the trial. The consent form will be written in Arabic.

27. Confidentiality:

All data, information, participant's personal information, family history, social and medical history will be stored in the files assigned to each patient with limited access to a minimum number of individuals necessary for quality control, audit, and analysis.

28. Declaration of interest:

This study is a part of a master's degree in Pediatric Dentistry, Faculty of Dentistry, Cairo University. No financial conflict of interests is confirmed. The study is self-funded by the principal investigator.

29. Access to data:

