The investigator will be given access to data sets. All data sets will be password protected. To ensure confidentiality, data dispersed to project team members will be blinded of any identifying participant information.

30. post-trial care:

The investigator will offer full mouth treatment, post-operative care, and preventive measures to all participants.

31. Dissemination policy:

The Thesis defense will be done as the study is a part of the requirements for a master's degree in Pediatric Dentistry. Also, the results of the study will be published in Journals.

V. Appendices**Appendix 1: Chart filled for each patient in this trial:**

Patient name:

Patient ID:

Tested material:

Age:

sex:

Address:

Telephone:

Chief complain of the patient:

Pretreatment medications:

Participating tooth:

Date of material application:

Follow up		1ry outcomes assessment clinical assessment (survival rate)		2ry outcomes assessment Radiographic assessment			Final assessment “success or failure”
Time after	Date	1- Spontaneous pain	2- Swelling	3- Internal root resorption	4 - External root resorption	5- Periapical radiolucency	
3m	/ /20						
6m	/ /20						

VI. References:

- 1- izGuven SD. *Success Rates of Pulpotomies in Primary Molars Using Calcium SilicateBased Materials: A Randomized Control Trial. Biomed Res Int.* 2017;2017:7.
- 3- *Use of collagen as a biomaterial: An update - researchgate. (n.d.). Retrieved March 6, 2022, from* https://www.researchgate.net/publication/258204888_Use_of_collagen_as_a_biomaterial_An_update
- 5- J. Camilleri. “Hydration characteristics of biodentine and theracal used as pulp capping materials.” *Dent Mater.* 2014;30:709–715.

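### The primary radiographic outcome does not name furcation (inter-radicular) radiolucency, so a primary molar with that sign alone meets the written definition of success

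*Protocol*

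**What the plan says.** The protocol defines or records the radiographic outcome in four places.

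- **Section 12, primary outcome:** "Absence of periapical radiolucency and internal/ external root resorption", scored as binary on a periapical film.
- **Section 7, PICO table:** the primary outcome is "Absence of internal root resorption" and nothing else.
- **Section 13, schedule:** "Periapical radiograph to check the absence of periapical radiolucency, internal/ external root resorption".
- **Appendix 1, chart:** three radiographic columns, for internal resorption, external resorption and, last, "5- Periapical radiolucency". A column for an overall success-or-failure assessment follows, with no rule for completing it.

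Section 18 has two blinded assessors score independently and settle differences by consensus. It adds no radiographic criterion. The secondary outcome in section 12 is "Survival rate (absence of any complication or complementary treatment) in terms of" spontaneous pain and swelling; the schedule row also mentions a sinus. The teeth are described in section 10 as "Bilaterally Carious vital primary molars with reversible pulpitis", and section 15 narrows recruitment to lower molars.

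**The concern.** A primary molar has a furcation. In section 11 the pulp is removed down to the canal orifices and the dressing is placed over the stumps in the pulp chamber, so the treated site lies just above the inter-radicular bone. An outcome confined to the apex and to root resorption leaves out the bone nearest the intervention.

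Three things are at stake. Teeth with a furcation lesion alone count as successes, which overstates success in whichever arm they occur. Fewer failures are recorded, so the comparison carries less information. If one material fails in the furcation more often than the other, the primary outcome does not show it. A statistical analysis plan cannot repair this afterwards, because the protocol fixes the components and prints the form, and a sign that was not recorded cannot be analysed.

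**Working it through.** **Step 1. Apply the written rule.** Take a tooth with inter-radicular radiolucency, no periapical radiolucency, no internal or external resorption, no pain, no swelling and no sinus.

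| Place in the protocol | Signs named | Result for this tooth |
|---|---|---|
| Section 12, primary | periapical radiolucency, internal resorption, external resorption | success |
| Section 7, PICO primary | internal resorption | success |
| Section 13, radiograph row | the same three signs as section 12 | no listed sign present |
| Appendix 1, radiographic columns | the same three signs | all absent |
| Appendix 1, final column | no rule given | assessor's judgement |
| Section 12, secondary | spontaneous pain, swelling | no failure |

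A furcation lesion that comes with any of the three signs is already a failure under section 12. The gap concerns isolated lesions only.

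**Step 2. Effect on the recorded rates.** The protocol gives no event rates, effect size or sample size (section 14 says only that the calculation is still to be made), so there is no stated figure to reproduce. The inputs below are assumptions: true radiographic failure of p1 = 12% in one arm and p2 = 6% in the other, with a share s1 or s2 of each arm's failures being furcation-only.

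Recorded failure in arm i = p_i × (1 - s_i).

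With an equal share s in both arms:

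| s | Recorded rates | Absolute difference | Risk ratio |
|---|---|---|---|
| 0 | 12% vs 6% | 6 points | 2 |
| 0.10 | 12 × 0.90 = 10.8% vs 6 × 0.90 = 5.4% | 5.4 points | 2 |
| 0.25 | 12 × 0.75 = 9% vs 6 × 0.75 = 4.5% | 4.5 points | 2 |
| 0.50 | 12 × 0.50 = 6% vs 6 × 0.50 = 3% | 3 points | 2 |

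At s = 0.5, success is overstated by 6 points in one arm and 3 in the other. At s = 0.25, the figures are 3 and 1.5 points.

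**Step 3. Precision of the ratio.** For n teeth per arm, and ignoring the within-child pairing of the split-mouth design, n × Var(log RR) = (1 - p1)/p1 + (1 - p2)/p2.

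- s = 0: 0.88/0.12 + 0.94/0.06 = 7.33 + 15.67 = 23.0.
- s = 0.25: 0.91/0.09 + 0.955/0.045 = 10.11 + 21.22 = 31.3. The standard error is √(31.3/23.0) = 1.17 times as large.
- s = 0.5: 0.94/0.06 + 0.97/0.03 = 15.67 + 32.33 = 48.0. The standard error is √(48.0/23.0) = 1.44 times as large.

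**Step 4. Unequal shares.** The recorded risk ratio is (p1/p2) × (1 - s1)/(1 - s2).

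- s1 = 0.5, s2 = 0.25: 6% vs 4.5%, ratio 1.33.
- s1 = 0.25, s2 = 0.5: 9% vs 3%, ratio 3.

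The true ratio is 2 in both cases, so the bias can go either way.

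**The case against.** The best defence has four parts.

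**The assessor is not forced to call the tooth a success.** A reader might infer that the lesion cannot be recorded at all. The documents do not support that. Appendix 1 has the final success-or-failure column, which is not said to be the sum of the columns before it, and an assessor could also read periapical loosely enough to include the furcation. Section 22 provides for a failed pulpotomy ("retreatment of the tooth through partial pulpectomy and tooth will be removed from the trial") without defining failure. This part stands, but none of these routes names the sign. Two independent assessors could score the same film differently, and their consensus would have no written criterion.

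**Floor perforation does not support the point.** Section 22 lists "Perforation of pulpal wall or floor" as a foreseen harm, and a reader might infer that such teeth are scored as successes because perforation shows in the furcation. The same entry takes a repaired tooth out of the trial and otherwise has the tooth extracted. Recognised perforations therefore do not reach the primary outcome.

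**Frequency and timing are unknown.** It is tempting to say that furcation change is the main or earliest failure pattern, or the one most likely to be seen within 6 months. The protocol says nothing about failure patterns. The anatomical reasoning is sound; any frequency is an assumption.

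**The comparison is not necessarily biased.** Section 20 plans a measure it calls risk reduction and abbreviates R.R., which may be absolute or relative. If it is a ratio of failure risks and the share is equal in both arms, the estimate is unchanged. That is correct, but precision is still lost, the absolute difference still shrinks, and nothing in the protocol shows that two different materials would have equal shares.

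**Conclusion.** The point holds in a limited form. Nowhere does the protocol name furcation radiolucency, and under every stated version of the primary outcome an isolated furcation lesion meets the definition of success. The chart gives it no column and leaves the overall call undefined.

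The size cannot be established from the documents. It depends wholly on the furcation-only share s: negligible if s is near zero, and a halving of the recorded absolute difference at s = 0.5. The claim that the treatment effect is distorted on every scale does not hold, because the risk ratio is preserved when s is equal in both arms. The change is worth making because the gap is in the primary outcome, the correction is nearly free, and the sample size, which depends on the event rate under this definition, has still to be calculated.

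**What to change.** Define the primary outcome as absence of periapical or furcation (inter-radicular) radiolucency and absence of internal or external root resorption. Use that definition in section 12, the PICO table in section 7 and the radiograph row of the schedule in section 13. Add a furcation radiolucency column to Appendix 1, and state how the final success-or-failure column follows from the signs before it.

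The PICO table must be included. Otherwise the protocol keeps a primary outcome of internal resorption only, under which the furcation lesion is still a success. The same edit is the occasion to reconcile which signs are primary, since Appendix 1 labels the radiographic signs secondary and section 12 makes them primary.

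The cost is one phrase in three places, one chart column and one line of rule. The planned films and the planned two assessors suffice, provided the films show the furcation area. The downside is a slightly lower reported success rate.

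### Survival is defined by any complication or additional treatment, but the visit items and the chart can miss interval events, and a retreated tooth is removed without being counted as a failure

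*Protocol*

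**What the plan says.** Section 12 (Outcomes) gives the first secondary outcome as "Survival rate (absence of any complication or complementary treatment) in terms of" two components. Pain is a "Binary outcome measured with direct questioning to the patient". Swelling is a "Binary outcome measured visually by intraoral/extraoral examination".

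Section 7 sets the horizon: "Time of follow up:6 months". Section 18 sets the clinical time points: "Plans for assessment and collection of outcomes will be at 3 and 6 months clinically". It adds palpation and percussion to the visual examination. The section 13 schedule has no contact between the treatment visit and month 3, and none between months 3 and 6.

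Section 19 names the data record: "Data will be recorded on a diagnostic chart for each patient separately". In Appendix 1 the follow-up part of that chart has a 3-month row and a 6-month row. The survival block has two cells per row, for spontaneous pain and swelling, and each row ends with an overall success-or-failure cell.

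Section 22 (Harms) says of a failed pulpotomy: "retreatment of the tooth through partial pulpectomy and tooth will be removed from the trial". Section 23 gives the supervisors oversight that extends to the reporting of complications and how they were treated.

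**The concern.** The definition is cumulative: one complication or one additional treatment at any time in the six months ends survival. The measurements are tied to two visit days. Swelling judged by eye shows only what is there that day. The pain question has no stated period and is put to children aged 4 to 7, with no question to the parent specified. Additional treatment, which the definition names, has no cell on the chart.

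The rule for retreated teeth pulls another way. Retreatment after failure is a plain case of additional treatment, so under section 12 the tooth has not survived. Section 22 removes it and does not say how it is counted.

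At stake is whether the reported survival rate is the one defined. Both gaps push it upward. The outcome may also carry more weight than section 12 suggests, because Appendix 1 heads the survival block "1ry outcomes assessment clinical assessment (survival rate", which labels it primary.

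**Working it through.** The protocol states no survival rate, event rate, sample size or effect size, so there is no figure to reproduce. The check sets the passages side by side and then illustrates on assumed figures.

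**What becomes of an interval event if the plan is followed as written**

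| Event between visits | Under the section 12 definition | What the plan records |
|---|---|---|
| Swelling that settles by itself | Not survived | Absent (judged visually on the day) |
| Swelling treated short of section 22 retreatment, quiet at the visit | Not survived | Absent; no cell for the treatment |
| Pain that has stopped | Not survived | Undetermined: depends on how the child understands a question without a recall period |
| Pulpotomy failure with retreatment | Not survived | Tooth removed (section 22); not stated whether it is a failure or leaves the denominator |

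**Illustration (assumed figures, not from the protocol)**

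Let F be the true failures per 100 teeth and s the share of them that occur between visits and are hidden by one of the two routes. True survival is (100 − F)/100; with F = 10 it is 90%.

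- Route A, recorded as absent: (100 − F + sF)/100
- Route B, removed and dropped from the denominator: (100 − F)/(100 − sF)

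| s | Route A | Route B |
|---|---|---|
| 25% | (90 + 2.5)/100 = 92.5% | 90/97.5 = 92.3% |
| 50% | (90 + 5)/100 = 95.0% | 90/95 = 94.7% |
| 100% | (90 + 10)/100 = 100% | 90/90 = 100% |

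The two routes overstate survival by nearly the same amount, so removing the tooth does not protect the estimate unless it is also counted as a failure.

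**Effect on the comparison.** Under Route A the observed failures are F(1 − s). If s is the same for both materials, the ratio of failures is unchanged, since F₁(1 − s)/[F₂(1 − s)] = F₁/F₂, and the difference shrinks to (F₁ − F₂)(1 − s). If s differs between materials, both measures are distorted, in favour of the material with the larger hidden share. The protocol gives no ground for saying whether s differs.

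**The case against.** A reader might infer that every treated interval complication is scored as survival. Section 22 does not support that: a tooth retreated for failure is removed, so for it the mechanism is possible exclusion. Being recorded as event-free applies only to a complication that settles, to treatment short of that retreatment, or to treatment the team never learns of.

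A reader might also infer that every interval event is missed. That goes too far for pain. A question about spontaneous pain can bring out history, and without a recall period the text supports today's pain no better than pain since treatment. The point is ambiguity, not certain loss.

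Nor can one say that the supervisors would be unaware of such events. Section 23 covers reporting of complications, and section 5 has the co-supervisor check for harms. Neither is tied to the survival outcome. Bur breakage and perforation of the pulpal wall or floor (section 22) arise during the procedure and do not bear on events between visits.

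It can further be argued that the two named items are the operational definition and that the chart matches them; that the success-or-failure cell can carry an overall judgement; and that event rows belong in operational forms or a statistical analysis plan. The match with the chart is real, but it leaves the wider wording about additional treatment unmeasured. The success-or-failure cell sits in the same two visit rows, and no rule makes an interval event a failure. Section 19 makes this chart the data record, and an analysis plan cannot recover what was not collected.

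**Conclusion.** The point holds in a limited form. The survival definition is wider than the two items and the chart that measure it: no recall period is fixed, and additional treatment and interval events have no field. Swelling that has resolved, or was treated short of retreatment, is recorded as absent; interval pain may be missed. The removal rule in section 22 conflicts with section 12 and inflates survival if the tooth leaves the denominator.

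The direction for each survival rate is upward. The size cannot be computed, because the protocol gives no event rates; the percentages above follow from assumed F and s and show only how the two routes behave. A reader might go on to infer that the comparison is biased in favour of one material, for instance through early reactions to the collagen dressing. Nothing in the protocol supports that; it would require the hidden share to differ between materials, which is unknown.

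This should be corrected before enrolment, since events that are not collected cannot be reliably recovered later.

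**What to change.** - **Section 12:** define pain, swelling and complementary treatment as occurring at any time since the previous visit (for month 3, since the treatment visit).
- **Sections 13 and 18:** at 3 and 6 months put that question to the parent as well as the child.
- **Appendix 1:** add, for each tooth, an interval-event entry (date, sign, treatment given) and a yes/no cell for complementary treatment. It must be by tooth because section 11 places both materials in the same child.
- **Counting rule:** state that any such entry, including section 22 retreatment for pulpotomy failure, is a survival failure and that the tooth stays in the denominator.
- **Section 22:** reconcile the removal wording with this rule for the analysis. This concerns counting only, not how a failed tooth is managed.

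The cost is a reworded question and a few chart fields, with no extra visit or staff. The reported survival rate will probably be slightly lower, and interval events will rest partly on parental recall.
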